8.2.2 Modified intent-to-treat population

For all efficacy endpoint analyses, a mITT population will be used, comprising all patients who received at least one dose of derazantinib or atezolizumab, and have at least one post-baseline imaging assessment in accordance with RECIST 1.1, or documented clinical

progression (every effort should be made to objectively assess radiographic progression). Non-evaluable patients will be replaced.

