13. Tumor assessments performed as SoC prior to obtaining informed consent and within 28 days of the first dose of study treatment on C1D1 may be used rather than repeating tests. The first on-study tumor imaging assessments will be performed after 9 weeks on study, and will be repeated every 9 weeks (± 7) from C1D1 (i.e., at C4D1, C7D1, C10D1) and every 12 weeks (± 7) from C10D1 (i.e., at C14D1, C18D1, etc.) thereafter (with additional scans as clinically indicated and as per RECIST 1.1 criteria) until disease progression, death, or loss of follow-up. A tumor assessment should be performed at the End-of-Treatment visit only if the prior scan was not done within 4 weeks (28 days) prior to this visit, or if the prior scan did not show radiographic disease progression. The same radiographic procedure as used at the SV must be used throughout the study for each patient to follow target lesions, and results must be reviewed by the Investigator before dosing at the next cycle. Imaging timing should be based on the first dose at C1D1, should follow calendar days, and should not be adjusted for delays in cycle starts.
14. For pre-dose PK blood sampling at C1D15 (**all substudies**), and C1D8, C2D8 and C2D15 (**safety interim analysis patients in Substudies 3 and 5**), administer derazantinib at the study site.
15. Derazantinib PK blood (plasma) sampling will be performed according to the following schedule:
 - a. **Rich PK profiling - Applicable to safety interim analysis patients in Substudy 3 and 5 only:**
 - C1D1, prior to derazantinib dose, and 1 hour (± 5 minutes), 2 hours (± 5 minutes), 4 hours (± 15 minutes), 8 hours (± 30 minutes), 10 hours (± 30 minutes), 12 hours (± 30 minutes; prior to the second dose administration), 24 hours after first derazantinib administration (i.e., 12 hours post second dose administration but within 1 hour prior to the third dose).
 - C1D8, pre-dose (within 1 hour prior to the next dose), and 6–8 hours after derazantinib administration.
 - C1D15, pre-dose (within 1 hour prior to the next dose), and 6–8 hours after derazantinib administration.

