5.2. Modified Intent-to-treat (mITT) Population

For all efficacy endpoint analyses, a mITT population will be used, comprising all patients who received at least one dose of derazantinib or atezolizumab, and have at least one post-baseline imaging assessment in accordance with RECIST 1.1, or documented clinical progression (every effort should be made to objectively assess radiographic progression) or death. Non-evaluable patients will be replaced.

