 * If a CR is truly met at first time point, then any disease seen at a subsequent time point, even disease meeting PR criteria relative to baseline, makes the disease PD at that point (since disease must have reappeared after CR). Best response would depend on whether minimum duration for SD was met. However, sometimes 'CR' may be claimed when subsequent scans suggest small lesions were likely still present and in fact the patient had PR, not CR at the first time point. Under these circumstances, the original CR should be changed to PR and the best response is PR.

As specified in RECIST 1.1, repeated 'NE' time point assessments complicate best response determination. Should a CR/PR be followed by a NE response and then a CR/PR, then confirmed response would be achieved (as an example PR-NE-PR will be considered as a confirmed response).

Note that iRECIST criteria (an adaptation of RECIST 1.1 to account for the tumor response patterns seen with immunotherapeutic drugs ([Seymour 2017](#))) will also be considered in exploratory analyses.

Patients without efficacy assessments are considered non-responders, and included in the analysis.

Hypothesis testing (null hypothesis [H₀] versus alternative hypothesis [H_A]) will be performed at the interim and final analyses as specified below:

Substudy 1

H₀: p ≤ 0.21 versus H_A: p ≥ 0.34

If there are seven or fewer patients with an objective response (defined as a confirmed CR or PR) in the first 35 evaluable patients included in the interim analysis, the substudy will be stopped. If not, an additional 39 patients will be enrolled, for a total of 74 evaluable patients. The null hypothesis will be rejected if 22 or more objective responses are observed in these 74 patients.

Substudy 3

H₀: p ≤ 0.25 versus H_A: p ≥ 0.45

If there are four or fewer patients with an objective response (defined as a confirmed CR or PR) in the first 18 evaluable patients included in the interim analysis, the cohort will be stopped. If not, an additional 18 patients will be enrolled, for a total of 36 evaluable patients. The null hypothesis will be rejected if 14 or more objective responses are observed in these 36 patients (or if 10 or more responses are observed in

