6.3.2.3. Progression-Free Survival (All Substudies)

Progression-Free Survival (PFS) will be calculated as the time from cohort assignment by IWRS until disease progression as assessed by BICR, or death from any cause, whichever comes first. Patients who either have no baseline tumor evaluation or have no post- baseline tumor evaluation will be censored at date of cohort assignment by IWRS. Patients without disease progression will be censored at the date of their last tumor evaluation. Patients who discontinue treatment due to reasons other than disease progression by BICR or death will be censored in the PFS analyses as the date of their last tumor evaluation prior to EOT. Patients who progress or die after missing ≥ 2 consecutive scheduled tumor assessments will be censored at the date of the last tumor evaluation prior to progression or death. Any deaths occurring after end of treatment are not taken into account as a PFS event. Patients who stopped treatment without PD will be censored at their last scan prior to end of treatment. For patients with missing end of treatment visit date, a +7 day window compared to the maximum of last dose date, last on treatment visit date will be applied to create a tentative end of treatment visit date and a cut-off for death occurring after this date. The rules for censoring PFS are summarized in the table below:

Table 5: Censoring scheme for PFS

Situation	Date of progression or censoring	Outcome
No baseline or post-baseline tumor assessments	Randomization / Cohort assignment	Censored
Progression documented between scheduled visits	Date of radiological assessment of measured lesions	Progressed
No progression	Date of last radiological assessment of measured lesions	Censored
Treatment discontinuation for reasons other than disease progression by BICR or death	Date of last radiological assessment of measured lesions	Censored
Death before first PD assessment	Date of death	Progressed
Death between adequate assessment visits	Date of death	Progressed
Death or progression after more than one missed tumor assessment or after end of treatment	Date of last radiological assessment of measured lesions prior to progression or death	Censored

Additional sensitivity analyses will be conducted which consider alternative censoring methods as outlined in FDA guidelines ([FDA 2018](#), [FDA 2015](#)).

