A first sensitivity analysis will consider the same analysis as outlined in Table 5, but also considering clinical progression as an event (either clinical or radiographic progression will be considered as an event, rather than just radiographic).

A second sensitivity analysis will include all post end of treatment assessments, such that subjects who die or progress after end of treatment will be considered as an event, with censoring at the earliest of last scan performed / new anti-cancer treatment. The censoring scheme for this analysis is outlined in Table 6.

Table 6: Censoring scheme for PFS - sensitivity analysis 2

Situation	Date of progression or censoring	Outcome
No baseline or post-baseline tumor assessments	Randomization / Cohort assignment	Censored
Progression documented between scheduled visits	Date of radiological assessment of measured lesions	Progressed
No progression	Date of last scan performed / new anti-cancer treatment	Censored
Death before first PD assessment	Date of death	Progressed
Death between adequate assessment visits	Date of death	Progressed
Death or progression after more than one missed tumor assessment or after end of treatment	Date of death or progression	Progressed

A third sensitivity analysis (Table 7) uses a conservative approach by assigning the date of discontinuation, or missed visit as an event date.

Table 7: Censoring scheme for PFS - sensitivity analysis 3

Situation	Date of progression or censoring	Outcome
No baseline or post-baseline tumor assessments	Randomization / Cohort assignment	Censored
Progression documented between scheduled visits	Date of radiological assessment of measured lesions	Progressed
No progression, treatment ongoing	Date of last radiological assessment of measured lesions	Censored
Treatment discontinuation for reasons other than disease progression by BICR or death	Date of discontinuation	Progressed
Death before first PD assessment	Date of death	Progressed
Death between adequate assessment visits	Date of death	Progressed
Death or progression after more than one missed tumor assessment or after end of treatment	Date of first missed visit	Progressed

PFS will be analyzed using Kaplan-Meier methodology ([Kaplan & Meier 1958](#)). The median duration of PFS will be presented along with the 2-sided 95% CI. If they are calculable, the 25th and 75th percentiles and

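### SAP 6.3.2.3 gives two PFS outcomes, censored at day 0 or an event, for an on-treatment death before any post-baseline scan; secondarily, DOR has no alternative analysis for events after end of treatment

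*SAP*

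**What the plan says.** **PFS.** SAP 6.3.2.3 runs PFS from cohort assignment to BICR progression or death from any cause. Its text then censors patients who lack either scan: those with no baseline or no post-baseline "tumor evaluation will be censored at date of cohort assignment by IWRS". Tables 5, 6 and 7 each hold two relevant rows:

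- "No baseline or post-baseline tumor assessments": censored at randomization or cohort assignment.
- "Death before first PD assessment": progressed, at the date of death.

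Sensitivity analysis 1 reuses Table 5 and adds clinical progression. Sensitivity analysis 2 (Table 6) is built "such that subjects who die or progress after end of treatment will be considered as an event". Sensitivity analysis 3 uses Table 7. On scan timing, footnote 13 to SAP Table 1 says: "The first on-study tumor imaging assessments will be performed after 9 weeks on study".

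Protocol 8.3.4.2 also counts death from any cause as a PFS event, and also censors patients with no post-baseline scan, at first dose.

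**Population.** SAP 5.2 ends its mITT definition with "every effort should be made to objectively assess radiographic progression) or death. Non-evaluable patients will be replaced". Protocol 8.2.2 ends with "objectively assess radiographic progression). Non-evaluable patients will be replaced", without death.

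**DOR.** SAP 6.3.2.2 runs DOR to BICR progression or death, but censors both at the last tumor assessment if they fall after end of treatment (EOT). Protocol 8.3.4.2 censors responders who stop, are lost or die with no documented progression; it does not censor documented progression after EOT.

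**Declared changes.** SAP 6.8 lists only the dropped IPCW model.

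**The concern.** A patient who dies on treatment before about week 9 has no post-baseline scan. The text sends that patient to day 0, censored; the death row makes the same patient an event. Two programmers working from the same SAP could produce different PFS curves, and the choice could end up being made after the data are seen.

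The day-0 reading is also the wrong one in substance. Early death is the worst PFS outcome, and censoring it at day 0 removes the patient from every risk set. The ORR rule treats the same patient as a failure: "Patients without efficacy assessments are considered non-responders, and included in the analysis".

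For DOR the concern is narrower. Responders will be few, documented progression after EOT is set aside, and no second analysis shows what that does.

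**Working it through.** **1. Do the two rules really overlap?** Take an on-treatment death in week 6 with no post-baseline scan.

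| Rule | Applies? | Outcome |
|---|---|---|
| 6.3.2.3 text, no post-baseline scan | Yes | Censored, day 0 |
| Tables 5–7, row 1, read as the text explains it | Yes | Censored, day 0 |
| Tables 5–7, death before first progression assessment | Yes | Event, date of death |
| Two or more missed scans | No, none was due | – |
| Death after EOT | No | – |

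Row 1 alone could mean that both scans are missing, but the text makes either absence sufficient. Table 5's discontinuation row excepts death explicitly; row 1 does not. Because sensitivity analysis 1 reuses Table 5 and Tables 6 and 7 repeat both rows, no sensitivity analysis resolves the case.

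**2. Size for PFS.** Let N be the patients analysed, k the on-treatment deaths before the first scan, and e(t) the number event-free at a later time t. Assume no other censoring before those deaths.

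- Deaths counted: S(t) = e(t)/N.
- Deaths censored at day 0: S(t) = e(t)/(N−k).
- Ratio of the second to the first: N/(N−k). The risk sets are identical afterwards, so the ratio persists.

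Direct Kaplan–Meier on constructed data gave 1.0400 (N=26, k=1), 1.0833 (26, 2), 1.0588 (36, 2) and 1.0417 (50, 2), equal to N/(N−k).

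N comes from SAP 6.1.6. The documents give neither k nor a PFS rate, so k = 1 to 3 and a reported 6-month PFS of 35.0% are assumptions. With the deaths counted, 35.0 × (N−k)/N gives:

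| N (substudy) | k=1 | k=2 | k=3 | 95% half-width, points |
|---|---|---|---|---|
| 26 (5) | 33.7% | 32.3% | 31.0% | 18.3 |
| 36 (3) | 34.0% | 33.1% | 32.1% | 15.6 |
| 50 (each cohort of 4) | 34.3% | 33.6% | 32.9% | 13.2 |
| 74 (1) | 34.5% | 34.1% | 33.6% | 10.9 |

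The half-width is 1.96 × √(0.35 × 0.65/N). The overstatement runs from 35.0 − 34.5 = 0.5 to 35.0 − 31.0 = 4.0 points. If m other patients are also censored at day 0, the ratio is (N−m)/(N−m−k), slightly larger: with N=26, m=2, k=1, 35.0 × 23/24 = 33.5%.

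The median is less sensitive. With an assumed exponential median of 5 months in scanned patients, read at the scheduled scans, it stayed at 6.21 months in most cases and fell to 4.14 only with 4/26, 8/50 or 8/74 such deaths. With an assumed median of 3 months it did not move.

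**3. Size for DOR.** Take r responders, one of whom stops treatment, with no other censoring, and d other events by time t.

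- That patient has an event before t: S(t) = (r−1−d)/r.
- That patient is event-free at t: S(t) = (r−d)/r.
- That patient is censored after d₁ of the d events: S(t) = [(r−d₁)/r] × [(r−1−d)/(r−1−d₁)], which lies between the other two.

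The outer values differ by 1/r, so reclassifying one responder moves the curve by at most 1/r, in either direction. At the final rejection boundaries in SAP 6.1.6 this is 1/6 = 16.7 points (Substudy 5), 1/7 = 14.3 (a Substudy 4 cohort), 1/14 = 7.1 (Substudy 3) and 1/22 = 4.5 (Substudy 1). The smallest change is 0.

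**The case against.** The best answer is that Table 5 resolves itself. If row 1 governed unscanned deaths, the row for death before the first progression assessment would be empty or would duplicate the row for death between adequate visits. Reading the specific row over the general one fits the PFS definition. That is probably what was meant, and the fix adopts it; but the text says the opposite without exception, and nothing ranks text against table.

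Other limits stand:

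- A reader might infer that counting early death as a PFS event is an undeclared change. It is not: protocol 8.3.4.2 already pairs death from any cause with no-scan censoring, so the SAP inherited the tension.
- A reader might infer that SAP 5.2 created the affected group. Protocol 8.2.2 already admits unscanned patients with documented clinical progression, some of whom may die. The SAP widens the group.
- The move of the no-scan censoring date from first dose to cohort assignment is near-immaterial, since protocol 4.4 places assignment on C1D1 or as close as possible to dosing.
- The main PFS rule for events after EOT largely follows the protocol and is covered by sensitivity analysis 2.
- On DOR, the schedule has no imaging column after the End of Treatment visit and protocol Appendix 2 ties scans to treatment, although footnote 13 reads more broadly. Scans after EOT may be sparse. By-patient DOR listings and swimmer plots are planned, but they are not an alternative estimate.

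**Conclusion.** The PFS conflict is real and sits in the text and all three tables. Following the text overstates later PFS by N/(N−k), always upward: about 0.5 to 4.0 points for a reported 35.0% with assumed k of 1 to 3. That is well inside the sampling error, and the median would usually not move. It does not support a claim that PFS would be seriously misleading. It supports correcting a rule that is wrong as written, before database lock.

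The DOR point is secondary: a bound of 1/r per responder, direction unknown. The SAP 6.8 omissions are housekeeping.

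The ORR cut-offs do not change. It would still be too strong to say that ORR is untouched: mITT is the primary ORR population, so adding death changes who is evaluable and who is replaced.

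**What to change.** 1. In the 6.3.2.3 text and in row 1 of Tables 5 and 7, restrict no-scan censoring to patients without an on-treatment death; in Table 6, to patients without any death. An on-treatment death without a scan is then an event at the date of death. Describe this as a clarification of protocol 8.3.4.2, not a departure.
2. Keep the main DOR rule and add one sensitivity analysis mirroring Table 6: BICR progression and death after EOT count as events, with censoring at the last scan or new anti-cancer treatment.
3. List in SAP 6.8: death as a DOR event; censoring of documented progression after EOT in DOR; the explicit exclusion of deaths after EOT from PFS; and death in the mITT definition, noting its effect on who is evaluable for ORR.

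The cost is one clause of text, one row in three tables, one extra DOR analysis and the SAP 6.8 entries, with no new data collection. PFS may come out slightly less favourable; the DOR sensitivity result may go either way.

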6.3.2.2. Duration of Response (All Substudies)

Duration of Response (DOR) will be calculated from the first date of documented objective tumor response (confirmed CR or PR) to the date of disease progression as assessed by BICR or death. If a patient is discontinued or lost to follow-up with no documentation of PD, DOR is defined as the time from the date of first documented objective tumor response to the date of last tumor assessment as a censored value. PD or death post end of treatment will be censored at date of last tumor assessment as a censored value.

DoR will be derived only for patients who have the best overall response of CR or PR.

DOR will be analyzed using Kaplan-Meier methodology ([Kaplan & Meier 1958](#)). The median DOR will be presented along with the standard error and 2-sided 95% CI. If they are calculable, the 25th and 75th percentiles and the 2-sided 95% CIs around the percentiles will be presented. Kaplan-Meier estimates at 3, 6, 9 and 12 months will also be presented. The Kaplan-Meier survival curves will also be presented. For substudy 4 only comparisons between cohorts will be made by considering a hazard ratio, with associated 2-sided 95% confidence interval and p-value, from an unadjusted Cox proportional hazards model.

These analyses will be performed per cohort in substudies 1, 3, 4 and 5 and by dose level in substudy 2. The date of first dose, documented objective tumor response, disease progression, death, last tumor assessment, last contact and DOR days will be reported in a by-patient listing.

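### The main PFS and DOR analyses censor progression and death after end of treatment, which can lengthen the reported medians if patients who stop without confirmed progression fare worse

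*SAP*

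**What the plan says.** **PFS.** SAP 6.3.2.3 measures PFS from cohort assignment to BICR progression or death from any cause. It then states "Any deaths occurring after end of treatment are not taken into account as a PFS event" and "Patients who stopped treatment without PD will be censored at their last scan prior to end of treatment". In Table 5, the row "Death or progression after more than one missed tumor assessment or after end of treatment" is censored at the last radiological assessment before the event.

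**DOR.** SAP 6.3.2.2 counts progression or death as the event but adds: "PD or death post end of treatment will be censored at date of last tumor assessment as a censored value". The sentence before it censors any responder who is discontinued or lost to follow-up without documented PD.

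**Sensitivity analyses.** SAP 6.3.2.3 plans three for PFS. The first adds clinical progression. In the second (Table 6), "subjects who die or progress after end of treatment will be considered as an event". The third (Table 7) "uses a conservative approach by assigning the date of discontinuation, or missed visit as an event date". None is planned for DOR.

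**Protocol.** Section 8.3.4.2 already censors PFS when treatment stops for reasons other than BICR progression or death, and after two or more consecutive missed assessments. For DOR it censors every death without PD. The explicit exclusion of deaths after end of treatment appears only in the SAP. SAP 6.8 lists one change from the protocol, the dropped IPCW analysis.

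**Data collected.** Protocol 3.1.7, 4.5.2 and 5.2.3.1 follow patients for survival after treatment stops.

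**The concern.** Kaplan-Meier estimation treats a censored patient as having the same outlook as those still at risk. The site stops treatment, but the event needs BICR, so failing patients can be censored. Protocol 5.3.3.2.5 takes clinically unstable combination patients off treatment at the first site-assessed progression, without repeat imaging. Appendix 2 describes global deterioration that ends treatment without objective progression. Toxicity and investigator decision also end treatment (Protocol 3.1.5). The End of Treatment visit falls within 7 days of the last dose, so a death three weeks after stopping is not a PFS event. If no scan was done after baseline, the text has such patients' "tumor evaluation will be censored at date of cohort assignment by IWRS", so they contribute no follow-up at all.

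At stake are secondary endpoints: median PFS, 6-month PFS and DOR (Protocol 3.2.2), and the descriptive hazard ratios between the Substudy 4 cohorts. A regimen with more toxicity stops would have more patients censored this way, which matters when Substudy 5 explores a higher dose than Substudy 1.

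**Working it through.** The documents state no assumed PFS or DOR median, event count or rate of stopping without progression, so there is no figure of the plan's own to reproduce. The only related figure is that 15% of Substudy 2 patients permanently discontinued for an AE (Protocol 1.4.1.2). The scan schedule is from the documents: every 9 weeks to week 27, then every 12 weeks. All other inputs are assumptions.

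**Model A: prognosis changes at stopping.** PFS is exponential with on-treatment median M, so λ = ln 2 / M. A share d stops without BICR progression, at rate λd/(1-d). After stopping, the hazard is mλ. For M = 4 months, λ = 0.693/4 = 0.173 per month; for d = 30% the stopping rate is 0.173 × 0.30/0.70 = 0.074 per month. Table 5 is mimicked by censoring at the last scheduled scan before stopping, and compared with counting every event. Kaplan-Meier medians in months, 300,000 simulated patients per row:

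| M | d | m | All events | Table 5 | Difference |
|---|---|---|---|---|---|
| 4 | 15% | 1 | 3.99 | 3.88 | -0.1 |
| 4 | 15% | 2 | 3.83 | 3.88 | +0.1 |
| 4 | 15% | 4 | 3.65 | 3.88 | +0.2 |
| 4 | 30% | 1 | 4.00 | 3.71 | -0.3 |
| 4 | 30% | 2 | 3.62 | 3.69 | +0.1 |
| 4 | 30% | 4 | 3.28 | 3.69 | +0.4 |
| 6 | 15% | 1 | 6.00 | 5.88 | -0.1 |
| 6 | 15% | 2 | 5.75 | 5.88 | +0.1 |
| 6 | 15% | 4 | 5.47 | 5.88 | +0.4 |
| 6 | 30% | 1 | 5.99 | 5.70 | -0.3 |
| 6 | 30% | 2 | 5.44 | 5.71 | +0.3 |
| 6 | 30% | 4 | 4.92 | 5.69 | +0.8 |

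With m = 1 the shift is negative because censoring goes back to the last scan and discards event-free time before stopping. If stoppers do better (m = 0.5), Table 5 shortens the median by 0.3 to 0.8 months. Six-month PFS for M = 4, d = 30%, m = 4 is 0.33 under Table 5 against 0.26 with all events counted. If events are dated only on the scan grid, the median did not move in most scenarios and the shift shows in the 6-month rate instead.

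**Model B: the event follows soon after stopping.** The true median is 4.0 months. A share d stops at a uniform 50% to 95% of the patient's own event time and is censored at the last prior scan. Table 5 then reports 4.3 months at d = 10%, 4.5 at 15%, 4.6 to 4.7 at 20% and 5.1 at 30%. At 30% the shift is 5.1 - 4.0 = +1.1 months. Six-month PFS rises from 0.35 to between 0.38 (d = 10%) and 0.44 (d = 30%).

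**Comparing remedies under Model B.** The adverse case for any remedy is no scans after end of treatment, all deaths known and no new therapy. Median survival after progression is assumed to be 1 to 6 months:

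| d | True | Table 5 | Table 6 | Table 6 events, but censored after ≥ 2 missed assessments |
|---|---|---|---|---|
| 15% | 4.0 | 4.5 | 4.3 to 4.8 | 4.2 to 4.4 |
| 30% | 4.0 | 5.1 | 4.5 to 5.8 | 4.3 to 4.8 |

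Table 6 as written can be further from the truth than Table 5, because a death long after the last scan stands in for an unseen progression. Keeping the missed-assessment rule limits this.

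**The case against.** **The direction is not established.** A reader might infer that the rule certainly inflates the medians. The documents do not support that: they say nothing on how often patients stop without BICR progression or how they then fare, and Model A reverses the sign when stopping is unrelated to prognosis. Model B builds in poor prognosis. This stands.

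**Table 6 is not an unbiased replacement.** A reader might infer that it is, since it counts the missing events. But the documents disagree on imaging after treatment. Footnote 13 of Table 1 (both documents) continues scans "until disease progression, death, or loss of follow-up". The Table 1 grid marks no imaging after the End of Treatment visit, Protocol 5.3.3.2.3 asks only for best efforts around discontinuation, and Appendix 2 ties scheduled scans to being on treatment. Deaths will be known; progression off treatment may not be. This stands.

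**The shift is small against the noise.** With a true median of 4.0 months and no censoring, 95% of sample medians fall in 2.2 to 6.6 months at n = 26 and 2.8 to 5.5 at n = 74. No decision rule uses PFS or DOR, and the external benchmarks in the protocol are for ORR. This limits the importance, but a systematic shift is not excused by a wide interval.

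**PFS is already bracketed by three sensitivity analyses.** True for PFS. It does not help DOR.

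**Conclusion.** The concern holds in conditional form. The main PFS analysis and DOR set aside collected events that fall within the SAP's own endpoint definitions, and the documents describe routes by which failing patients reach that censoring. Informative censoring is plausible but not demonstrated.

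With a true or on-treatment median of 4 to 6 months and 15% to 30% stopping without BICR progression, the shift in median PFS runs from about -0.3 months (stopping unrelated to prognosis) to about +1.1 months (event soon after stopping). It would be more negative if stoppers do better than average. These figures rest on assumed inputs and apply to PFS; no DOR figure was computed. ORR and its two-stage decisions are untouched. The gap without any mitigation is DOR. This is an inexpensive improvement to secondary endpoints, not a flaw in the primary analysis.

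**What to change.** 1. **Main PFS analysis (SAP 6.3.2.3):** count BICR progression or death after end of treatment as an event. Keep the protocol's censoring after two or more consecutive missed assessments, and censor at the last scan before new anti-cancer therapy. Keep Table 5 as a sensitivity analysis.
2. **DOR (SAP 6.3.2.2):** apply the same rule. Both sentences need changing, the one on patients discontinued or lost to follow-up and the one on events after end of treatment. Reconcile the result with Protocol 8.3.4.2, which censors death without PD.
3. **SAP 6.8:** list and justify the departure from Protocol 8.3.4.2.
4. **Reporting:** tabulate censored patients by reason.
5. **Imaging:** reconcile Table 1 footnote 13 (both documents) with the Table 1 grid, Protocol 5.3.3.2.3 and Appendix 2, since how many later progressions are seen depends on this.
6. **Table 5:** reconcile the row that counts a death before the first PD assessment as an event with the text that censors patients without a post-baseline scan at cohort assignment.

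The cost is SAP wording, one extra DOR derivation, a justified departure from the protocol's censoring text, and probably slightly less favourable medians. Some dependence on prognosis will remain, because switching therapy or missing scans may itself reflect decline.
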